	
follow-up or end of study, whichever comes first. End of study is defined in Section 5.4 of Protocol Amendment 3. Dose interruptions or reductions may be required following potential drug-associated toxicities.
 
CCI [REDACTED]
 
 
○ For participants who discontinue study treatment for reasons other than PD, disease evaluations will continue to be performed every 3 weeks (<math>\pm 3</math> days) until confirmed (documented) PD, death, start of a new anticancer treatment, withdrawal of consent, or end of the study, whichever occurs first. In case of PD, participants will be followed to ascertain survival status CCI [REDACTED] every 12 weeks (<math>\pm 14</math> days) until withdrawal of consent, lost to follow-up, death or the end of the study.
 
● The final PFS analysis (primary analysis) will be conducted at the time of observing approximately 151 PFS events.
 
● A participant is considered to have completed the study if they are followed until death or end of study.
 
● End of study is defined as when the planned 250 deaths for final OS analysis have occurred, or when all participants have died or are lost to follow up or have withdrawn consent, whichever occurs first. At the first OS interim analysis (~40% OS information fraction), the study will not be stopped regardless of the results. GSK will continue to collect the OS data to conduct the 2nd OS interim analysis to test for efficacy at ~70% OS information fraction. If OS is significant at 70% IF, OS data will continue to be collected until all participants have died, are lost to follow up, or withdrawn consent, or for 2 years after the final OS analysis at 70% IF, whichever occurs first.
 

Study intervention
	
 
● Arm 1: Single agent Belantamab mafodotin. Belantamab mafodotin will be administered intravenously at 2.5 mg/kg on Day 1 (D1) of a Q3W schedule (e.g., 21-day cycle).
 
● Arm 2: Pomalidomide and low-dose dexamethasone (Pom/Dex). Pomalidomide will be administered orally at the approved starting dose of 4 mg daily on Days 1 to 21 of each 28-day cycle, with dexamethasone administered orally at a dose of 40 mg once weekly (Days 1, 8, 15, and 22). For participants over 75 years old, dexamethasone should be administered at the lower dose of 20 mg once weekly (Days 1, 8, 15, and 22).
 

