A separate summary will be provided for study intervention-related AEs. A study intervention-related AE is defined as an AE for which the investigator classifies the possible relationship to study intervention as “Yes”. A worst-case scenario approach will be taken to handle missing relatedness data, i.e. the summary table will include events with the relationship to study intervention as ‘Yes’ or missing. The summary table will be displayed in two ways: 1) by maximum grade sorted by PT in descending order and 2) in descending order by SOC and PT.

A summary of cumulative incidence of AE by number of cycles (<=1, <=2, <=4, <=6, <=8, <=10, Any) received at first occurrence will be provided.

In addition, AEs of maximum grade of 3 or higher will be summarized separately by PT.

All SAEs will be tabulated based on the number and percentage of participants who experienced the event. Separate summaries will also be provided for study intervention-related SAEs. The summary tables will be displayed by PT. The summary of all SAEs will also be created by SOC and PT. In addition, a summary of cumulative incidence of SAE by number of cycles (<=1, <=2, <=4, <=6, <=8, <=10, Any) received at first occurrence will be provided.

A study intervention-related SAE is defined as an SAE for which the investigator classifies the relationship to study intervention as “Yes”. A worst-case scenario approach will be taken to handle missing data, i.e. the summary table will include events with the relationship to study intervention as ‘Yes’ or missing.

A summary of non-serious AEs that occurred in 5% of the participants or above will be provided (no rounding for the percentage will be used in terms of 5% threshold, e.g., event with 4.9% incidence rate should not be included in this table). The summary will be displayed by SOC and PT.

All AEs will be listed. Additionally, a listing of subject IDs for each individual AE will be produced. Separate supportive listings with participant-level details will be generated for fatal and non-fatal SAEs, respectively. The relationship between MedDRA SOC, PT, and Verbatim Text will be listed.

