level for the maximum grade, i.e. a participant will only be counted once as the worst case from all the events experienced by the participant. For action taken to an event, a participant will be counted once under each action, e.g. if a participant has an event leading to both study intervention discontinuation and dose reduction, the participants will be counted once under both actions.

An overview summary of corneal events (CTCAE), including counts and percentages of participants with any AE, AEs related to study intervention, Grade 3 and 4 AEs, Grade 3 and 4 AEs related to study intervention, AEs leading to permanent discontinuation of study intervention, study intervention related AEs leading to permanent discontinuation of study intervention, AE leading to dose reductions, AEs leading to dose delays, SAEs, SAEs related to study intervention will be produced. Unless otherwise specified, AEs will be summarized by treatment arms. AEs related to pomalidomide and dexamethasone separately, OR pomalidomide and dexamethasone in combo will all be considered as AEs related to the pom/dex regimen and summarized under the pom/dex treatment arm.

For each of these AESI, a summary of cumulative incidence by number of cycles ( $\leq 1$ ,  $\leq 2$ ,  $\leq 4$ ,  $\leq 6$ ,  $\leq 8$ ,  $\leq 10$ , Any) received at first occurrence will be provided.

For thrombocytopenia, number and percentage of participants with grade 3 or 4 platelet count decreased (based on lab data) and concomitant grade 2 or above bleeding event will be summarized. A bleeding event will be considered as concomitant only if the start date is within  $\pm 3$  days of the lab event.

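### AE and SAE cumulative incidence is tabulated by cycle count, although a planned cycle is 21 days for belantamab mafodotin and 28 days for pom/dex, and no day-based version is planned

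*SAP*

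**What the plan says.** SAP section 4.5.2 plans "A summary of cumulative incidence of AE by number of cycles", and later "a summary of cumulative incidence of SAE by number of cycles". The axis is the "number of cycles (<=1, <=2, <=4, <=6, <=8, <=10, Any) received at first occurrence". Section 4.5.2.1 plans "a summary of cumulative incidence by number of cycles" with the same cuts for corneal events, thrombocytopenia and infusion-related reactions. Section 4.5.2 makes AE summaries by treatment arm unless stated otherwise, and these displays state nothing else.

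Section 1.2 gives belantamab mafodotin "on Day 1 (D1) of a Q3W schedule (e.g., 21-day cycle") and pomalidomide "on Days 1 to 21 of each 28-day cycle".

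Three other provisions bear on the point:

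- Section 4.5.1 lets cycles stretch. Belantamab delays are counted from the previous dose plus 21 days and tabulated as 1-21, 22-42 and >42 days. A pom/dex cycle runs to the day before the next one starts.
- Section 6.2.3 counts AEs as treatment-emergent until 70 days after treatment stops or until new anti-cancer therapy starts.
- Section 4.5.2.1 reports onset in days for corneal events and thrombocytopenia, with a last category of >63 days, and in hours for infusion-related reactions. General AEs and SAEs have no day-based onset display.

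**The concern.** A cumulative-incidence table by arm invites a row-by-row comparison. Here a row fixes the number of cycles, not time at risk, and the arms have different planned cycle lengths. A between-arm difference in a row may come from the event hazard, the cycle length or dose delays, and the table cannot separate them. Delays make this harder to read: a toxicity that postpones dosing also lengthens the window in which that toxicity is counted.

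What is at stake is the reading of a descriptive safety display. Safety and tolerability against pom/dex is a secondary objective (section 1.1.1) and the trial is open-label. No hypothesis test uses these tables.

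**Working it through.** The SAP gives no window lengths for these cuts, so there is no figure of its own to reproduce.

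**Step 1. Planned windows.** Window = cut × planned cycle length (21 or 28 days, section 1.2).

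| Cut (cycles) | Belantamab (days) | Pom/dex (days) | Excess (days) | Ratio |
|---|---|---|---|---|
| <=1 | 21 | 28 | 7 | 1.333 |
| <=2 | 42 | 56 | 14 | 1.333 |
| <=4 | 84 | 112 | 28 | 1.333 |
| <=6 | 126 | 168 | 42 | 1.333 |
| <=8 | 168 | 224 | 56 | 1.333 |
| <=10 | 210 | 280 | 70 | 1.333 |

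Any has no cycle window.

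**Step 2. Idealised effect.** With an equal constant hazard, no delays and everyone treated through the cut, a belantamab incidence p becomes 1 − (1 − p)^(28/21) for pom/dex. So 20%, 30% and 50% become 25.7%, 37.8% and 60.3%, which is +5.7, +7.8 and +10.3 points.

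**Step 3. Add discontinuation and the tail.** Assumptions:

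- Equal event hazard λ = −ln(0.8)/84 = 0.00266 per day, so 20% have the event by day 84.
- Treatment duration exponential, with medians taken from the section 5.2 PFS assumptions: 4 months for pom/dex and 7 months for belantamab. At 30.44 days per month, μ = 0.00569 and 0.00325 per day.
- Crude percentages and no delays. Events in the 70-day tail fall under the last cycle received. Administrative censoring and new therapy are ignored.

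With cycle length L, cut c and F(x) = 1 − exp(−λx), the tabulated incidence is

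∫₀^(cL) μ·exp(−μt)·F(t + 70) dt + exp(−μcL)·F(cL).

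| Cut | Belantamab % | Pom/dex % | Difference, with tail | Difference, on-treatment events only |
|---|---|---|---|---|
| <=1 | 6.3 | 9.0 | +2.7 | +1.4 |
| <=2 | 11.9 | 16.2 | +4.3 | +2.0 |
| <=4 | 21.2 | 26.4 | +5.1 | +1.7 |
| <=6 | 28.5 | 32.7 | +4.2 | +0.4 |
| <=8 | 34.2 | 36.7 | +2.5 | −1.4 |
| <=10 | 38.6 | 39.2 | +0.6 | −3.2 |
| Any | 54.3 | 43.4 | −10.9 | −13.1 |

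The last column replaces t + 70 by t. The hazards are equal, so every non-zero difference is an artefact. The negative values at late cuts and at Any come from shorter pom/dex exposure.

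**Step 4. Belantamab delays, pom/dex undelayed.** With mean delay d per cycle the window ratio is 28/(21 + d): 1.00 at 7 days, 0.80 at 14 and 0.67 at 21. One 42-day delay gives 28c/(21c + 42): 0.89 at 4 cycles, 1.00 at 6 and 1.11 at 10. In the step 3 model with the tail, a belantamab cycle of 28 days (mean delay 7) brings the 4-cycle difference to +0.1 points, and 35 days (mean delay 14) brings it to −4.2.

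**Step 5. Common day windows, same model.** The crude incidence by day D counts events up to the earlier of D and t + 70. Pom/dex minus belantamab is 0.0 at days 21 and 42, −0.1 at 84, −0.7 at 126, −1.7 at 168 and −2.8 at 210.

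**The case against.** The strongest reply is that nothing here is misstated. Asking after how many courses an event first appears is legitimate, the axis is labelled in cycles, and the cycle lengths are given. The main AE tables (overview, preferred term, system organ class, maximum grade, grade 3 or higher, SAEs) use no cycle cuts. Treatment duration is reported in both arms. Corneal events and thrombocytopenia already have day-based onset, and infusion-related reactions have no useful comparator in an oral regimen. All of this stands. It limits the point to the AE and SAE cumulative tables, and less importantly to the AESI tables. The AESI day categories stop at >63 days, three planned belantamab cycles, so they do not cover the cuts from 4 cycles upward.

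A reader might infer that the display favours belantamab mafodotin at every cut, by the 5.7 to 10.3 points of step 2. The documents do not support that. Those figures need everyone to stay on treatment without delay, whereas the SAP tabulates delays, treats until progression and assumes different median PFS by arm. Under those conditions the difference shrinks, vanishes or reverses, depending on the cut. Any has no cycle window at all.

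It is also fair that crude counts in common day windows do not remove the effect of unequal exposure at late cuts (−2.8 points at day 210).

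**Conclusion.** The point holds as a comparability defect in descriptive safety tables. The one-third excess in planned window at the six numbered cuts follows directly from the SAP. The distortion does not have a fixed size or sign. At planned cycle lengths with the 70-day tail it inflates pom/dex at early cuts, by about 5 points at 4 cycles when 20% have the event by 84 days. It fades to under 1 point at 10 cycles and reverses at Any. Those figures rest on equal constant hazards, exponential treatment duration at the SAP's median PFS, crude percentages and no delays. A mean belantamab delay of 7 to 14 days per cycle removes or reverses the 4-cycle gap. A systematic bias towards the test drug is not shown, and no confirmatory result is affected. This is a cheap improvement.

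**What to change.** In sections 4.5.2 and 4.5.2.1, base the between-arm cumulative-incidence tables for AEs, SAEs and AESIs other than infusion-related reactions on common windows from first dose, for example <=21, 42, 84, 126, 168 and 210 days and Any. Preferably estimate them with censoring at the end of the treatment-emergent window, so that differing exposure does not distort the late cuts. State that this treats discontinuation as uninformative, and say how death is handled. Keep the by-cycle tables as within-arm displays, and say under which cycle an event after the last dose is counted.

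The cost is SAP wording and one changed or additional table shell. Section 6.2.4 already defines study day from first dose, so no new data are needed.

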#### 4.5.2.1. Adverse Events of Special Interest

The following will be considered adverse events of special interest (AESI) for the purpose of analyses: corneal events (CTCAE), thrombocytopenia and infusion-related reactions.

For corneal events (CTCAE), thrombocytopenia and infusion-related reactions (IRR), in addition to events identified and collected in eCRF, a comprehensive list of MedDRA terms based on clinical review will be used to identify each type of event. Specifically for IRR, events identified by the comprehensive list of MedDRA terms based on clinical review would only be considered IRR if the event was reported on an infusion day after the start of infusion or within 24 hours following end of infusion, AND led to a temporary interruption or prolongation of infusion time or treatment withdrawal. Changes to the MedDRA dictionary could occur between the start of the study and the time of reporting and/or emerging data from on-going studies may highlight additional adverse events of interest, therefore the list of terms to be used for each event of interest and the specific events of interest will be based on the SRT agreements in place at the time of reporting.

Summaries of the number and percentage of participants with these events will be provided for each type of events separately by preferred term and maximum grade. The time to onset and duration of first occurrence for each type of events will be summarized using summary statistics mean, standard deviation, median, minimum value, and maximum. The number and percentage of participants who have time to onset of first occurrence in categories of (1-21, 22-42, 43-63, >63 days) will be reported for corneal events (CTCAE) and thrombocytopenia. The number and percentage of participants who have time to onset of first occurrence in categories of (0-6, >6-12, >12-18, >18-24, >24 hours) will be reported for infusion-related reactions. The number and percentage of participants who have duration of first occurrence in categories of (1-21, 22-42, 43-63, 64-84, 85-105, >105 days) will be reported for corneal events (CTCAE) and thrombocytopenia. The number and percentage of participants who have duration of first occurrence in categories of (0-12, >12-24, >24 hours) will be reported for infusion-related reactions. For an AESI which is based on a single adverse event term, the onset and duration will be calculated based on the start and end dates of the single term. For an AESI which is based on multiple adverse event terms, the onset and duration will be calculated by looking across all terms for the AESIs. The derived start date is identified as the onset of any term defined as the AESI. The derived end date is identified as last end date for any terms once all concurrent terms for the AESI have resolved, i.e., the first time a subject is free of any adverse event term defined as the AESI.

The summary of event characteristics will be provided for each AESI respectively, including number of participants with any event, number of events, number of participants with any event that is serious, number of participants with any event that is related to study intervention, number of occurrences (One, Two, Three or more), maximum grade, maximum grade for events related to study intervention, outcomes and the action taken for the event. The percentage will be calculated in two ways, one with number of participants with event as the denominator and the other with total number of participants as the denominator. The worst-case approach will be applied at participant

level for the maximum grade, i.e. a participant will only be counted once as the worst case from all the events experienced by the participant. For action taken to an event, a participant will be counted once under each action, e.g. if a participant has an event leading to both study intervention discontinuation and dose reduction, the participants will be counted once under both actions.

An overview summary of corneal events (CTCAE), including counts and percentages of participants with any AE, AEs related to study intervention, Grade 3 and 4 AEs, Grade 3 and 4 AEs related to study intervention, AEs leading to permanent discontinuation of study intervention, study intervention related AEs leading to permanent discontinuation of study intervention, AE leading to dose reductions, AEs leading to dose delays, SAEs, SAEs related to study intervention will be produced. Unless otherwise specified, AEs will be summarized by treatment arms. AEs related to pomalidomide and dexamethasone separately, OR pomalidomide and dexamethasone in combo will all be considered as AEs related to the pom/dex regimen and summarized under the pom/dex treatment arm.

For each of these AESI, a summary of cumulative incidence by number of cycles ( $\leq 1$ ,  $\leq 2$ ,  $\leq 4$ ,  $\leq 6$ ,  $\leq 8$ ,  $\leq 10$ , Any) received at first occurrence will be provided.

For thrombocytopenia, number and percentage of participants with grade 3 or 4 platelet count decreased (based on lab data) and concomitant grade 2 or above bleeding event will be summarized. A bleeding event will be considered as concomitant only if the start date is within  $\pm 3$  days of the lab event.

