### 4.5.3. Ocular Findings on Ophthalmic Exam

#### 4.5.3.1. Ocular Exam and Visual Acuity

As outlined in study protocol (GlaxoSmithKline Document Number: [2017N336101\\_00](#)) Schedule of Activities (Section 2 of the protocol), ocular exams are scheduled at screening, while on treatment, and at end of treatment for participants in both arms. Ocular exams in follow-up period (if needed) will only be conducted for Arm 1 (belantamab mafodotin). The ocular findings and visual acuity from ocular exams will be summarized descriptively:

- **From baseline to last follow-up, the following analyses will be performed**

- i. Visual acuity

- The best corrected visual acuity (BCVA) summary will be based on the Logarithm of the Minimum Angle of Resolution (logMAR score), where:
 
$$\text{logMAR score} = -\log_{10}(\text{Snellen Acuity Score})$$
- The following categories of logMAR score changes from baseline are defined: No change/improved vision is defined as a change from baseline  $<0.12$ ; a possible worsened vision is defined as a change from baseline  $\geq 0.12$  to  $<0.3$ ; a definite worsened vision is defined as a change from baseline  $\geq 0.3$  logMAR score.
- A summary of characteristics of worsened vision (logMAR Score change from baseline  $\geq 0.12$ ) by subject will be provided, including time to onset of first occurrence: summary statistics and frequency/percentage in categories (1-21, 22-42, 43-63, 64-105, >105 days); outcome of first occurrence, duration of first occurrence: summary statistics and frequency/percentage in categories (1-21, 22-42, 43-63, 64-105, >105 days); number of occurrences based on participants with worsened vision; outcome post treatment exposure; time to resolution post treatment exposure, outcome of last event. The duration is defined as time from onset of worsened vision to the first time the subject is free of worsened vision (i.e. free of  $\geq 0.12$  logMAR Score change from

baseline). It requires at least one day gap between the resolution of all worsened vision from first occurrence to the onset of second occurrence.

- In addition, a summary of worst change from baseline (based on the eye with worst change) in BCVA Score (logMAR Score) will be provided for categories “increase  $\geq 0.12$  to  $< 0.3$ ”, “increase  $\geq 0.3$  to  $< 0.6$ ”, “increase  $\geq 0.6$ ”.
- Shift table for visual acuity from baseline to worst case post-baseline by eye (R/L) will be provided

ii. Corneal Exam

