#### 4.5.3.2. Corneal Events Based on Keratopathy and Visual Acuity Scale (KVA Scale)

For ocular exam visits based on the ocular worksheet under the original protocol, KVA grade is not expected to be collected. For ocular exam visits based on the ocular worksheet under the protocol amendment 1, KVA grade is expected to be collected. Analyses in this section will be based on collected / investigator reported KVA scale only.

Unless otherwise specified, for the following analyses, corneal events (KVA scale) will be summarized by treatment arms based at subject level (subject level KVA grade at each visit is defined as worse-eye grade at each visit).

An overview summary of corneal events (KVA scale) will be provided, including numbers and percentages of participants with any corneal events (KVA scale), and corneal events Grade 2 or above and Grade 3 or above (KVA scale).

In addition to the overview summary described above, an additional overview summary of corneal events (KVA scale) will be provided for only those participants enrolled under protocol amendment 1, including numbers and percentages of participants with any corneal events (KVA scale) leading to permanent discontinuation of study intervention, corneal events (KVA scale) leading to dose reductions, and corneal events (KVA scale) leading to dose delays.

A summary of characteristics of corneal events (KVA scale) of grade 2 or above by subject will be provided, including time to onset of first occurrence: summary statistics and frequency/percentage in categories (1-21, 22-42, 43-63, 64-105, >105 days); outcome of first occurrence, duration of first occurrence: summary statistics and frequency/percentage in categories (1-21, 22-42, 43-63, 64-105, >105 days); number of occurrences based on participants with corneal events (KVA scale) of grade 2 or above; outcome post treatment exposure; time to resolution post treatment exposure; outcome of last event. The duration is defined as time from onset of any corneal events (KVA scale) of grade 2 or above to the first time the subject is free of overall KVA grade  $\geq 2$ . It requires at least one day gap between the resolution of all events from first occurrence to the onset of second occurrence.

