**6.2.7. Handling of Partial Dates**

Element	Reporting Detail		
General	
 
• Partial dates will be displayed as captured in participant listing displays.
 
• However, where necessary, display macros may impute dates as temporary variables for sorting data in listings only. In addition, partial dates may be imputed for ‘slotting’ data to study phases or for specific analysis purposes as outlined below.
 
• Imputed partial dates will not be used to derive study day, time to onset or duration (e.g., time to onset or duration of adverse events), or elapsed time variables (e.g., time since diagnosis). In addition, imputed dates are not used for deriving the last contact date in overall survival analysis dataset.
 
		
Adverse Events	
 
• Partial dates for AE recorded in the CRF will be imputed using the following conventions: 
 
 Missing start day	First of the month will be used unless this is before the start date of study treatment; in this case the study	
 
 
 
	Missing start day	First of the month will be used unless this is before the start date of study treatment; in this case the study
Missing start day	First of the month will be used unless this is before the start date of study treatment; in this case the study		

Element	Reporting Detail	
		treatment start date will be used and hence the event is considered on-treatment
	Missing start day and month	No Imputation
	Missing end day	Last day of the month will be used.
	Missing end day and month	No Imputation
	Completely missing start/end date	No imputation
Concomitant Medications/ Medical History	
 
Partial dates for any concomitant medications recorded in the CRF will be imputed using the following convention:
 
	
	Missing start day	A '01' will be used for the day
	Missing start day and month	A '01' will be used for the day and 'Jan' will be used for the month
	Missing end day	A '28/29/30/31' will be used for the day (dependent on the month and year).
	Missing end day and month	A '31' will be used for the day and 'Dec' will be used for the month.
	Completely missing start/end date	No imputation

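### Durations of corneal events, thrombocytopenia, worsened vision and KVA grade 2 or above findings end only at observed resolution and get plain statistics, with no rule for unresolved events, so reported durations are likely to be too short

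*SAP*

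**What the plan says.** SAP Section 4.5.2.1 covers adverse events of special interest. It states that the time to onset and "duration of first occurrence for each type of events will be summarized using summary statistics mean, standard deviation, median", minimum and maximum, and it adds day categories for corneal events (CTCAE) and thrombocytopenia. For an event of special interest defined by one term, "the onset and duration will be calculated based on the start and end dates of the single term". Where several terms define it, the end is "the first time a subject is free of any adverse event term defined as the AESI".

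Section 6.2.7 states that "Imputed partial dates will not be used to derive study day, time to onset or duration". Its adverse event row headed "Completely missing start/end date" allows no imputation.

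Section 4.5.3.1 gives worsened vision summary statistics and day categories: "The duration is defined as time from onset of worsened vision to the first time the subject is free of worsened vision". Section 4.5.3.2 does the same on the KVA scale: "The duration is defined as time from onset of any corneal events (KVA scale) of grade 2 or above to the first time" the participant is free of grade 2 or above. It repeats the pattern for corneal exam findings and for visual acuity. Both sections also list time to resolution after treatment exposure without naming a method, so the descriptive default of Section 4.1.1 applies.

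None of these sections gives a rule for an event that has not resolved, or mentions censoring. Section 4.3.2.1 does use Kaplan-Meier for duration of response and time to progression.

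**The concern.** A duration that ends at resolution is right-censored when the participant reaches the data cut-off, is lost or dies with the event still present. A plain mean or median has no place for such a record, which must be dropped or given an artificial end. Long events are the most likely to be unresolved, so the summary is selected towards short ones.

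Unresolved events are to be expected. Table 8 in Section 4.7 puts the primary analysis at about 25 months and the first dose of the 320th participant at about 21 months, so the last entrants have about 4 months of follow-up. The highest duration category is above 105 days.

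Ocular findings are a named secondary safety endpoint, and corneal events are an event of special interest. Readers will look to these tables to learn how long the effects last, and the error would make the harm look shorter than it is.

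**Working it through.** The SAP gives no duration and no unresolved share, so there is no plan figure to reproduce. The size has to be shown over a range of assumptions.

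**Inputs from the SAP.** Entry uniform to month 21 and cut-off at month 25 (Section 4.7, Table 8); Arm 1 median OS 19 months and 5% loss per year (Section 5.2).

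**Assumed.** Time to onset exponential with median 45 days; exponential event duration with true median 30, 90 or 180 days; follow-up independent of duration.

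**Simulation, 400,000 participants per scenario (medians and means in days).**

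| True median | Unresolved | Median, dropped | Median, cut at last follow-up | True mean | Mean, dropped | Mean, cut |
|---|---|---|---|---|---|---|
| 30 | 7% | 28 | 28 | 43 | 40 | 40 |
| 90 | 23% | 67 | 73 | 130 | 93 | 100 |
| 180 | 41% | 99 | 118 | 260 | 132 | 153 |

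**Closed-form check.** If duration and censoring are both exponential and a share u is unresolved, the dropped and the cut data have the same distribution, with median m × (1 − u). For m = 90: u = 10% gives 81, 20% gives 72, 30% gives 63 and 40% gives 54. At u = 23%, 90 × 0.77 = 69, between the simulated 67 and 73.

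**Shape, true median 90.** Less skewed durations (Weibull shape 1.5) give 79 (dropped) or 78 (cut). More skewed durations (shape 0.7) give 49 or 69.

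**What counts as the truth.** Death is treated as censoring in the 90-day benchmark. About half of the unresolved events in this scenario end in death (23.3% unresolved, of which 11.3 percentage points are in living participants). Two other targets, with death median 19 × 30.44 = 578 days:

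- Time lived with the event, to resolution or death: median 1 / (1/90 + 1/578) = 78 days.
- Cumulative incidence of resolution with death competing: the resolving share is (1/90) / (1/90 + 1/578) = 0.865, and 0.865 × (1 − exp(−t × ln 2 / 78)) = 0.5 at about t = 97 days.

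Against 90 days the shortfall is 26% (67) or 19% (73). Against 78 days it is 14% or 6%.

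**Share above 105 days, true median 90.** The true share is 45%. The table would show 33% with resolved events as denominator, 25% with all participants who had the event, or 36% if unresolved events are cut.

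**Where the median is not biased.** If all unresolved events were truncated at one common time beyond the median, the median would be right. With true median 90 and truncation at 180 days the median is 90, though the mean is 97 instead of 130. Staggered entry does not produce a common time.

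**Sampling error.** With about 91 events (assumed) and true median 90, the dropped median averages 67 (SD 11) and the Kaplan-Meier median 91 (SD 15).

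**The case against.** The strongest case on the other side has four parts.

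- **The SAP nowhere says that unresolved events are dropped.** Section 6.2.7 concerns partial and missing dates, not events ongoing at cut-off, and Section 1 leaves data handling conventions to the Output and Programming Specification. This stands in part. Dropping is an inference for the CTCAE-based events, and for the exam-based durations the handling is open. But Section 4.5.2.1 has itself chosen the statistics, and with staggered follow-up neither dropping nor cutting rescues a plain mean.
- **The 90-day benchmark counts time after death.** This stands, and against time lived with the event the shortfall is much smaller. Which target is meant should be stated.
- **Unresolved events are not hidden.** Outcome rows are planned in Sections 4.5.2.1, 4.5.3.1 and 4.5.3.2, and the Section 4.1.1 default includes n. Section 4.5.2.1 also gives two denominators for its event-characteristics summary. With all participants who had the event as denominator, the share resolved by day 105 is nearly right (51% against 52.5% by cumulative incidence). This helps a careful reader but does not correct the mean or median, and neither the two-denominator rule nor any other is tied to the duration categories.
- **The size is assumed.** This stands. One duration model was applied to quite different events, and median follow-up after onset in it is about 256 days, so short events are hardly affected.

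A reader might infer that every one of these durations is certain to be understated, or that both handlings always shorten the median. The documents do not support that: the exam-based rule is not stated, and truncation beyond the median leaves the median intact. Nor do they support any effect on the PFS or OS tests.

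**Conclusion.** The point holds as a minor one. For corneal events (CTCAE) and thrombocytopenia, the plan on its natural reading leaves unresolved events without a duration and summarises the rest, which biases mean and median short. For worsened vision and the KVA durations the rule is missing: dropping gives the same bias, while cutting at last follow-up shortens the mean and usually the median.

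The effect runs from negligible when most events last about a month to material when they last about three months or more. These sizes assume follow-up independent of duration and the onset and duration models above. The consequence is confined to descriptive safety tables. Infusion-related reactions, categorised in hours, raise no such problem.

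**What to change.** For these durations, and for time to resolution after treatment exposure in Sections 4.5.3.1 and 4.5.3.2:

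- Report a Kaplan-Meier median with 95% CI and the number censored. Censor events unresolved in living participants at the last relevant eye exam or adverse event follow-up.
- State how death before resolution is handled, for example by cumulative incidence of resolution with death as a competing event.
- Label any plain summary 'resolved events only' and give its n.
- State the denominator of the day categories.

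The cost is a few extra descriptive tables from data already collected, and reported durations that are somewhat longer.

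One assumption remains, that censoring at the last exam is non-informative. It is doubtful here, because Section 4.5.3.1 says "Ocular exams in follow-up period (if needed) will only be conducted for Arm 1", and it should be noted beside the tables. In an assumed scenario in which the rate at which exam follow-up ends is doubled or halved according to whether the event lasts more or less than 90 days, the Kaplan-Meier median is off by 7 to 9 days and the plain medians by 29 to 33. The change therefore improves matters even then, but does not remove all bias.
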